#### **7.4.4 Guidance for the treatment of subjects who develop an acute coronary syndrome and those who require percutaneous coronary intervention with stenting - amended**

 Study medication should be temporarily interrupted in patients who require anticoagulant or DAPT because of an ACS event or for percutaneous coronary intervention (PCI) with stenting. Peri-procedurally, standard antiplatelet therapy, including ASA and clopidogrel (or other P2Y12 antagonists such as prasugrel or ticagrelor) can be administered according to usual practice. Study ASA may be continued. Standard anticoagulant therapy can be initiated without regard to the timing of the most recent dose of study medication because the dose of rivaroxaban being tested in this trial is significantly lower than the 15 or 20 mg dose administered for stroke prevention in non-valvular atrial fibrillation and the half-life of rivaroxaban is short, only 5-13 hours.

Following the procedure, the decision and timing to resume study medication are at the discretion of the treating physician and the investigator. If medically indicated, study medication may be used along with DAPT with clopidogrel as described in section 8.1, or interrupted until patient no longer requires DAPT.

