### Discontinuation of Study Drug for a Vascular Procedure

**Table 8–1** depicts the approximate equivalent dose of subcutaneous enoxaparin (mg/kg) relative to rivaroxaban 2.5 mg at given time points following its administration, and should be used to assist the investigator in deciding which dose of enoxaparin or equivalent dose of another antithrombotic agent to administer in the event when a patient may have to undergo an emergency interventional coronary procedure or pharmacologic reperfusion while receiving study drug.

**Table 8–1: Comparative antithrombotic effect at given time points following rivaroxaban 2.5 mg administration to subcutaneous enoxaparin doses**

Time after 2.5 mg Rivaroxaban Administration	Equivalent Enoxaparin Dose
3 h	0.15 mg/kg
6 h	0.1 mg/kg
> 9 h	0 mg/kg

Source: [Mega et al. 2012]

When thrombolysis is required within 3 hours of the last study drug administration, it may be necessary to unblind the patient at the discretion of the investigator to estimate the dose of enoxaparin to be administered; in the case the patient is in the rivaroxaban treatment group, the subcutaneous dose of enoxaparin should be adopted as given in **Table 8–1**.

In case of urgent PCI for acute ischemic event, the investigator should discontinue study medication and initiate therapy with non-study ASA prior to PCI with non-enteric coated formulation. The loading dose of non-study ASA may be considered. In addition, consider intravenous administration of 0.5 mg/kg of enoxaparin or its antithrombotic equivalent in patients who undergo PCI. In the event that a patient requires a non-emergency revascularization procedure (PCI or CABG), study medication should be stopped approximately 24 hours before the procedure, if possible, and appropriate anticoagulant or antiplatelet therapy should be instituted as medically indicated (including DAPT).

 Depending on the bleeding risk, the patient may, at the discretion of the managing physician, resume study medication thereafter, but no earlier than approximately 12 hours after the arterial sheath has been removed (for patients undergoing PCI) or after the post-procedural drains have been removed (for patients undergoing CABG surgery), and the last dose of parenteral anticoagulant therapy has been administered.

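### Sections 7.4.4 and 8.1 treat residual study-drug effect differently in coronary emergencies, and Table 8-1 neither covers its own trigger window nor keeps one meaning

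*Protocol*

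**What the plan says.** **Protocol 7.4.4** covers patients who develop an acute coronary syndrome (ACS) or need percutaneous coronary intervention (PCI) with stenting. It calls for temporary interruption of study medication where an anticoagulant or dual antiplatelet therapy is required, and adds: "Standard anticoagulant therapy can be initiated without regard to the timing of the most recent dose of study medication". Two reasons are given: the tested dose is well below the 15 or 20 mg used in atrial fibrillation, and "the half-life of rivaroxaban is short, only 5-13 hours".

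**Protocol 8.1, under Discontinuation of Study Drug for a Vascular Procedure**, applies when a patient may have to "undergo an emergency interventional coronary procedure or pharmacologic reperfusion while receiving study drug". It contains four relevant statements.

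- Table 8-1 "depicts the approximate equivalent dose of subcutaneous enoxaparin (mg/kg) relative to rivaroxaban 2.5 mg at given time points following its administration".
- The table "should be used to assist the investigator in deciding which dose of enoxaparin or equivalent dose of another antithrombotic agent to administer".
- "When thrombolysis is required within 3 hours of the last study drug administration, it may be necessary to unblind the patient", at the investigator's discretion, in order to estimate the enoxaparin dose. If the patient turns out to be on rivaroxaban, "the subcutaneous dose of enoxaparin should be adopted as given in" Table 8-1.
- For urgent PCI, a single intravenous figure of 0.5 mg/kg enoxaparin, or its equivalent, is offered for consideration. Time since the last study dose is not mentioned.

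Table 8-1, whose first column is headed "Time after 2.5 mg Rivaroxaban Administration", has three rows: 3 h, 0.15 mg/kg; 6 h, 0.1 mg/kg; more than 9 h, 0 mg/kg.

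**The concern.** The two sections meet in one patient: someone on blinded study drug with an ACS who needs emergency coronary treatment. Section 7.4.4 presents the time of the last dose as something the physician can set aside. Section 8.1 makes it the index of a dosing aid and, in one situation, a reason to consider breaking the blind. The protocol does not say which section governs.

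Section 8.1 also has two internal problems. The situation that may prompt unblinding lies in a time range for which the table has no entry. And the column changes role between its introduction and its use, so a physician reading it under time pressure has to work out what the figure stands for.

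At stake are consistent emergency anticoagulation across sites, in a trial where section 3.4 names bleeding as the prevailing risk of treatment, and the avoidance of unblinding that yields no usable information. Section 7.5 confines unblinding to medical necessity, so a prompt to unblind should rest on guidance that can be followed.

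**Working it through.** No sample size, event count or error rate is involved, and the plan states no figure to reproduce. The check is a comparison of the current text plus a count of table rows.

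**Step 1. The two sections side by side**

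| Question | 7.4.4 | 8.1, Discontinuation of Study Drug for a Vascular Procedure |
|---|---|---|
| Setting | ACS; PCI with stenting | Emergency coronary intervention; pharmacologic reperfusion |
| Role of time since last dose | Can be disregarded when starting anticoagulation | Index of Table 8-1, an aid to choosing the dose; absent from the urgent-PCI sentence |
| Residual drug effect | Discounted (low dose, short half-life) | Non-zero equivalents at 3 h and 6 h |
| Unblinding | Not mentioned | Possible, for thrombolysis within 3 hours of a dose |

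The settings overlap for ACS patients having emergency coronary intervention. Section 8.1 thus contains both a time-indexed aid and a figure that is not time-indexed.

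**Step 2. Do cross-references settle it?** Section 7.4.4 refers to 8.1 only for dual antiplatelet therapy with clopidogrel. Section 8.1 refers to 7.4.4 in its clopidogrel text and in its bullet on non-study ASA. None of these links the timing statement to Table 8-1 or says which prevails.

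**Step 3. Does the table cover its trigger?** The trigger is thrombolysis at time t within 3 hours of the last dose.

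- Rows with t < 3 h: 0 of 3.
- Rows at the boundary, t = 3 h: 1 of 3 (0.15 mg/kg).
- Rows outside the window: 2 of 3 (6 h and more than 9 h).

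There is also no entry between 3 h and 6 h, or from above 6 h up to and including 9 h.

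**Step 4. What does the column mean?** It falls from 0.15 to 0.1 to 0 mg/kg.

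- Read as the enoxaparin equivalent of the rivaroxaban effect still present, which is how it is introduced, the fall describes the drug wearing off.
- Read as the dose to give, which is how the thrombolysis sentence uses it, the same fall means the most enoxaparin soonest after rivaroxaban and none after 9 h.

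Both readings have text behind them, and they mean different things at the bedside.

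**Step 5. Context only.** With simple first-order decay, fraction remaining = 0.5^(t / half-life), and the stated half-life of 5 to 13 h:

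| t | half-life 5 h | half-life 13 h |
|---|---|---|
| 3 h | 66% | 85% |
| 6 h | 44% | 73% |
| 9 h | 29% | 62% |

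This ignores absorption and describes amount of drug, not effect, so it does not show that either section is right. It shows only that the half-life cited in 7.4.4 does not by itself make the two sections agree. The conclusion does not depend on it.

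**The case against.** The strongest reply is that the sections answer different questions. Section 7.4.4 says whether anticoagulation must wait; 8.1 helps decide how much to give. A physician could start at once and still consult the table. That stands in part: the two are not flatly incompatible. But the reasons given in 7.4.4 discount residual effect altogether, 8.1 treats it as relevant to dose, and no text joins them.

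The firm instruction is also narrow. In general the table only assists. Both the wording about adopting the tabulated dose and the unblinding prompt are confined to thrombolysis within 3 hours of a dose, and unblinding is at the investigator's discretion. Section 7.4.1 says the guidance does not replace clinical judgment, and 7.5 offers a 24-hour helpline. All of this stands and limits the reach of the problem. A reader could also apply the 3 h row to the whole window before it, but the text does not say so.

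Three stronger readings are tempting and are not supported.

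- *Two sites following different sections would treat the patient differently, and one would necessarily break the blind.* Different handling is possible, not certain. Unblinding is discretionary, and 8.1 does not prompt it for PCI.
- *A known share of emergencies is affected.* One might assume that events fall evenly over the 12-hour dosing interval and read shares off the table. The documents give neither the timing of emergencies nor a thrombolysis rate, the table has gaps, and the urgent-PCI sentence does not use time since dose.
- *Unblinding would compromise the endpoint.* In this clause it follows the event that prompts thrombolysis. It changes neither the time of that event nor its adjudication by a blinded committee.

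**Conclusion.** The concern holds as an internal inconsistency in emergency guidance. It has three parts: sections 7.4.4 and 8.1 treat residual study-drug effect differently for overlapping patients without reconciling text; Table 8-1 has no value below 3 h although the unblinding clause concerns that window; and the table's column is described as one thing and used as another.

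Its size can be stated only as coverage: 0 of 3 rows strictly inside the trigger window and 1 at its edge. The number of patients affected is unknown. Sample size, alpha, power and the primary analysis are unaffected. The relevance is to patient safety, avoidable unblinding and uniform site conduct. It should be fixed, but it is not a threat to the trial's inference.

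The conclusion rests on the current text of the two sections. Table 8-1 is derived from an attachment to another trial's protocol, which was not available, so its intended use there could not be checked.

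**What to change.** The sponsor's clinical team should:

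1. Reconcile 7.4.4 and 8.1 into one consistent instruction for ACS, emergency coronary intervention and reperfusion on study drug, with explicit cross-references, stating whether and how time since the last dose is to be considered. The urgent-PCI sentence belongs in the same reconciliation.
2. State what the Table 8-1 column represents and how it is to be used, and make the introductory sentence and the thrombolysis sentence agree with that.
3. Align the table's time range with the 3-hour trigger.
4. Keep or remove the discretionary unblinding prompt to match, consistent with 7.5.

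Which rule or dose is right is for the clinical team; no view is offered here.

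The cost is a text amendment to two sections and a letter to sites. No procedures, patients or analyses are added.

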#### **7.4.5 Guidance for the treatment of subjects who overdose on study medication**

A specific antidote for rivaroxaban is not available. If rivaroxaban overdose is suspected, the use of activated charcoal up to 8 hours after overdose to reduce absorption may be considered. Due to its low solubility, rivaroxaban absorption plateaus at doses of 50 mg and above, thus limiting exposure in the majority of patients.

#### **7.4.6 Guidance for the treatment of subjects who experience a major bleed**

The management of bleeding in patients receiving study medication is supportive, as rivaroxaban does not have a specific antidote. Temporary discontinuation of rivaroxaban is

 Text revised with Protocol Amendment 4 (change no. 17)

 Text revised with Protocol Amendment 4 (change no. 17)

expected to be sufficient to control bleeding in most cases because the drug half-life is only 5-13 hours. Local measures should be applied if needed to control bleeding (e.g., local pressure, endoscopy and injection of a bleeding vessel, as in embolization) and intravenous fluids and blood transfusion support should be provided as indicated. In the rare case of life-threatening bleeding, the investigator may consider obtaining advice from a hematologist. Animal studies suggest that both prothrombin complex concentrates, activated prothrombin complex concentrate (APCC), or recombinant factor VIIa partially restore hemostasis following treatment with factor Xa inhibitors such as rivaroxaban, and a randomized trial involving healthy patients treated with rivaroxaban has demonstrated that prothrombin complex concentrates reverse prolongation of the prothrombin time. Rivaroxaban cannot be dialyzed as it is highly protein bound.

#### **7.4.7 Guidance for the treatment of subjects who have impaired renal function**

Patients with impaired renal function (i.e.  $<60$  mL/min/1.73 m^2 but  $\geq 15$  mL/min/1.73 m^2) are eligible for the study (see Section 6.2). If a patient's eGFR is  $<30$  mL/min/1.73 m^2 prior to the index procedure, to enroll and randomize the patient the eGFR must be confirmed to ensure that the eGFR remains  $>15$  mL/min/1.73 m^2, at least 72 hours after the procedure.

During the study, in subjects with baseline eGFR  $<30$  mL/min/1.73 m^2, renal function should be monitored as per standard of care, tailored to the need of the subject. Study medication should be interrupted or permanently discontinued if the eGFR should fall below 15 mL/min/1.73 m^2.

#### **7.5 Blinding**

Study medication (rivaroxaban or matching placebo) assignment will be double-blind. Study treatment consists of study medication (rivaroxaban or matching placebo) in addition to study ASA. Additional details of emergency unblinding procedure can be found in the IxRS operation manual.

Unblinding should only be undertaken by the investigator when it is deemed medically necessary for the patient's safety and will be done via the IxRS system. If there is an uncertainty with respect to an unblinding decision, the investigator may contact the 24-hour Study Helpline (independent of the sponsor).

However, the Study Helpline contact should not delay emergency treatment of the patient. Examples that should trigger a Helpline discussion include life-threatening bleeding or bleeding requiring surgical intervention.

In compliance with applicable regulations, in the event of a SUSAR (see Section 9.6.1.4) related to the blinded treatment, the patient's treatment code will usually be unblinded before reporting to the health authorities, ethic committees, and investigators.

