## 9.4 Efficacy

### 9.4.1 Assessments and procedures at occurrence of primary efficacy events - amended

In addition to the interviews performed during the regular on-site visits, all study patients are requested to inform the site as soon as possible if they have been hospitalized (regardless of reason) or have experienced other significant adverse medical events in order to ensure timely identification of potential study efficacy outcome events and bleeding events.

The analysis of study efficacy outcome events will be based on events as adjudicated by the ICAC. Thus, the occurrence of study efficacy outcome events must be reported on Outcome/CV Event reporting forms, as described in the Endpoint Event Site Manual, and will undergo adjudication by the ICAC. All potential coronary ischemic events, cerebrovascular events and peripheral ischemic events should also be reported on the Outcome/CV Event reporting forms.

The following events will be assessed for primary efficacy (for event definition see Section 9.4.2):

- MI,
- Ischemic stroke,
- CV death,
- ALI,
- Major amputation due to a vascular etiology.

Please note that these study efficacy outcome in addition to bleeding events are exempted from AE/SAE reporting (see Section 9.6.1.3.3).

In addition to investigator-identified study efficacy outcome and bleeding events, safety data will be reviewed regularly for potential major vascular thrombotic events. In particular, Medical Dictionary for Regulatory Activities (MedDRA) preferred terms assigned to investigator-reported AEs will be screened for potential study efficacy outcome and bleeding events and investigators may then be asked to further investigate whether or not a study efficacy outcome or bleeding event occurred and potentially initiate the outcomes reporting process.

Study efficacy outcome events will be continuously collected from signing of the ICF to study end (including the post-study treatment follow-up call).

 Sentence added with Protocol Amendment 5 (change no. 6).

 Sentence revised with Protocol Amendment 5 (change no. 7).

 Sentence revised with Protocol Amendment 4 (change no. 23).

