### **9.6.1.3.3 Reporting of serious adverse events and study-specific exemptions - amended**

The common definition of SAEs is given in Section 9.6.1.1. Each SAE must be followed up until resolution or stabilization by submission of updated reports to the designated recipient.

The efficacy and safety outcomes in this study will be collected in the eCRF and regularly monitored by the IDMC during the entire course of the study in a timely adequate manner. Due to this targeted surveillance, no AE documentation and no expedited SAE reporting will be performed for these events. Consequently, they will neither be un-blinded nor reported to regulatory authorities, IECs, or investigators. The IDMC will periodically review and assess all safety data for imbalances in safety outcomes. It is believed that in this way patient safety can continue to be monitored throughout the duration of the trial, along with study integrity. If unexpected safety issues are identified, specific amendments will be implemented.

The following rules should be followed:

1. **Primary and secondary efficacy outcome events** occurring after randomization will not be recorded on the AE page and not be reported as SAEs to Sponsor's PV

 Cross-references added by Amendment 4 (change no. 17).

 Wording changed by Amendment 4 (change no. 17).

department, but they will be collected on the specific eCRF pages as an efficacy outcome event.

2. **Safety outcome events** (i.e., bleeding events occurring after signing of the ICF) will not be recorded on the AE page and not be reported as SAEs to Sponsor's PV department, but they will be collected on the specific eCRF pages as a safety outcome event.
3. **All other SAEs (including complications of efficacy or safety outcome events)** that fulfill the seriousness criteria provided in Section 9.6.1.1 need to be collected on the eCRF (AE page) and reported as SAEs to the PV department. All SAEs that fulfill SUSAR criteria will be reported to the concerned authorities by expedited means (see Section 9.6.1.4).
4. **Pregnancies** need to be captured and reported to the Sponsor's PV department within 24 hours, even if classified as non-serious (see Section 9.6.2).

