### **Sponsor's notification of the investigational site**

The Sponsor will inform all investigational sites about reported relevant events (e.g., SUSARs) according to all applicable regulations.

 No. 2 changed with Protocol Amendment 5 (change no. 7).

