#### **9.6.1.4      Expected adverse events**

For this study, the applicable reference document is the most current version of the Investigator's Brochure (IB).

Overview listings of frequent events that have occurred so far in the clinical development are shown in the current IB. If relevant new safety information is identified, the information will be integrated into an update of the IB and distributed to all participating sites.

The expectedness of AEs will be determined by the Sponsor according to the applicable reference document (IB) and according to all local regulations. All SAEs that fulfill the SUSAR criteria as defined by the International Conference on Harmonization (ICH) E2A Guideline will be reported to the concerned authorities by expedited means.

In compliance with applicable regulations, in the event of a SUSAR, the patient's treatment code will usually be unblinded before reporting to the competent authorities, IECs/IRBs. For reporting to investigators, the treatment blind, if possible, will be kept.

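### Protocol 7.5 and 9.6.1.4 set opposite defaults on whether SUSAR reports to investigators are unblinded, and the two should be aligned

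*Protocol*

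**What the plan says.** Protocol 7.5 allows an investigator to break the code only when this is medically necessary for the patient's safety, and through the IxRS. Its last paragraph then deals with expedited reporting: "in the event of a SUSAR (see Section 9.6.1.4) related to the blinded treatment", the "treatment code will usually be unblinded before reporting to the health authorities, ethic committees, and investigators".

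Section 9.6.1.4 (Expected adverse events) covers the same report. There the "treatment code will usually be unblinded before reporting to the competent authorities, IECs/IRBs", and investigators are not in the list. They have their own sentence: "For reporting to investigators, the treatment blind, if possible, will be kept".

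The paragraph in 9.6.1.3.3 on the sponsor's notification of the sites says who hears about such events: "The Sponsor will inform all investigational sites about reported relevant events (e.g., SUSARs) according to all applicable regulations".

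The same section takes the study's efficacy and safety outcomes out of this pathway: "they will neither be un-blinded nor reported to regulatory authorities, IECs, or investigators".

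**The concern.** Staff who prepare SUSAR reports have two current instructions for one task. If they follow 7.5 alone, the natural result is a report to investigators that is no longer blinded. Because SUSARs are notified to all sites, that could include the site treating the patient concerned.

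That site still has work to do that depends on the blind. Patients who stop study drug stay in follow-up (Protocol 6.3.1), and every randomized patient is in the efficacy analysis (10.2). For these patients the investigator:

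- decides whether study drug is interrupted, restarted or stopped (7.4.1, 8.1);
- judges the causality of adverse events (9.6.1.2.2);
- grades PAD symptom status (9.7.4);
- starts the adjudication process, since "the occurrence of study efficacy outcome events must be reported on Outcome/CV Event reporting forms" (9.4.1).

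Two analysis rules make this relevant to the results:

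- The primary safety analysis counts events up to 2 days after permanent discontinuation (10.3.1). A stop influenced by a known code would shorten that patient's safety window.
- The secondary efficacy analyses use investigator-reported events where no adjudication took place (SAP 6.2.6). The second endpoint in the hierarchy, unplanned index-limb revascularization, is itself a treatment decision.

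**Working it through.** No arithmetic decides this point. It depends on no alpha, power, effect size or event count. The check is a comparison of the current texts.

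**Step 1. Compare the two rules by recipient.**

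| Recipient of the SUSAR report | Protocol 7.5 | Protocol 9.6.1.4 | Agree? |
|---|---|---|---|
| Health authorities | unblinded, as a rule | unblinded, as a rule | yes |
| Ethics committees (IECs/IRBs) | unblinded, as a rule | unblinded, as a rule | yes |
| Investigators | unblinded, as a rule | blinded, if possible | no |

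The sentences are nearly identical apart from the investigators, which suggests a drafting slip in one of them.

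**Step 2. Ask whether the qualifiers reconcile them.** Section 7.5 is softened by *usually* and 9.6.1.4 by *if possible*. Each allows exceptions, but the starting points remain opposite: 7.5 starts from an unblinded report to investigators, 9.6.1.4 from a blinded one.

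**Step 3. Look for a text that settles it.** Amendments 4 and 5 (Protocol 15.1 and 15.2) change neither sentence. The SAP does not discuss SUSAR unblinding. No text says which section prevails. Section 7.5 only points to 9.6.1.4.

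**Step 4. Ask which rule fits the rest of the protocol.** The design is double-blind. Section 7.5 itself reserves site-level unblinding for medical necessity. Section 9.6.1.3.3 keeps outcome events blinded and names study integrity among its reasons. The 9.6.1.4 rule fits all three, and the inclusion of investigators in the last paragraph of 7.5 does not.

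**Step 5. Bound the reach.**

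- Post-randomization primary and secondary efficacy outcomes, and bleeding after consent, are outside expedited reporting (9.6.1.3.3). SUSARs can come only from the remaining serious events.
- That exemption has edges. Complications of outcome events remain reportable (9.6.1.3.3, rule 3), and in Japan outcome events are reported as adverse events or SAEs (SAP 6.4.1). Whether any of these becomes a SUSAR depends on expectedness and causality.
- Adjudication is blinded (Protocol 5 and 13.1.3), and the preferred terms of reported adverse events are screened for missed outcomes (9.4.1).
- Each patient whose code is disclosed is 1 of about 6,500, and 1 / 6,500 = 0.015%. If s patients have a SUSAR, the share is s / 6,500. The documents give no value for s, so the calculation stops there.

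**The case against.** The case for leaving the text alone is that both rules are conditional and that 7.5 sends the reader to 9.6.1.4, where the express rule for investigators stands. Someone who follows the cross-reference finds it. This shows how a careful reader could resolve the conflict. It does not remove it, because 7.5 states its own rule in full and a reader has no stated reason to treat it as overridden.

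A reader might infer several stronger things that the documents do not support:

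- **That each SUSAR certainly discloses a code to every site.** Section 7.5 says the code is broken before the report goes out. It does not say that the investigator's copy shows the code. The notification paragraph is tied to applicable regulations and does not mention codes. Disclosure is the natural reading of 7.5, not a stated fact.
- **That 7.5 is the governing section.** Nothing in the protocol ranks the two.
- **That the adjudication committee sees only what unblinded sites send.** A site would learn the code of the SUSAR patient, not of its other patients. All potential coronary, cerebrovascular and peripheral ischemic events must be reported, and the screening of adverse event terms is a backstop. It is a partial one, since it works from investigator-reported events and returns queries to the same investigators.
- **That a series of codes would teach sites which harms belong to the active drug.** This is conjecture, and bleeding, the main recognized risk, is exempt.
- **That investigators must always be kept blinded.** Section 9.6.1.4 says only if possible.

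**Conclusion.** The inconsistency is real and stands in current text: opposite defaults for the same report, with nothing to reconcile them. Following 7.5 as written could disclose treatment codes to the people who manage study drug and report events for the patients concerned.

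The likely effect on the results is small. The events that make up the primary efficacy and primary safety endpoints are largely outside this pathway, and adjudication is blinded. No bias in the hazard ratio and no effect on type I error or power can be calculated, because the documents give neither an expected nor an observed SUSAR count. A figure such as tens of SUSARs would be a guess, so the documents do not support a claim that the primary result is compromised.

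The conclusion rests on one assumption: that a report made to investigators after unblinding would show the code. If the sponsor's procedures already produce a blinded investigator copy, practice is sound and only the wording of 7.5 needs correcting. The change is worth making because the contradiction is certain and the remedy is short.

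**What to change.** In the last paragraph of Protocol 7.5, remove investigators from those who receive the report after the code is broken. Add the 9.6.1.4 rule with its qualifier, for example: *Reports to investigators are kept blinded where possible, subject to applicable regulations (see 9.6.1.4).* The qualifier should stay, since an absolute rule would be stricter than 9.6.1.4 and could conflict with local requirements. Emergency unblinding by the investigator through the IxRS is unchanged.

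The edit is about one sentence. It changes no analysis and adds no procedure beyond what 9.6.1.4 already foresees. Under 13.1.1, every amendment needs the principal investigator's signature and all required external approvals before it takes effect at a center, so this does not justify an amendment of its own. It should go into the next one.
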